### 3.4.5 Safety Analysis

Safety data will be summarized using the safety population. Missing data will not be imputed for safety analyses. With the exception of adverse events, safety results will be summarized by the CRF nominal study visits (i.e., Week 1, Week 2, Week 4, Week 8, Week 12, and Week 16). For subjects that prematurely discontinue treatment before Week 16 with an End of Treatment (EOT) assessment, that EOT will be used in analysis for the nominal protocol visit most closely matching the subject's visit schedule. Similarly, for patients with safety results at an unscheduled visit that unscheduled visit will be used in analysis for the nominal protocol visit most closely matching the subject's visit schedule. For all safety listings except adverse events, if a safety result does not fall within a scheduled visit window, that result will be included in the safety listings but not the safety table summaries.

Moreover, if retest values are available, all safety analyses should use the results closest to the target study day (e.g., Day 28 for Week 4, Day 56 for Week 8, etc.). If two values are equidistant from the target study day, the earliest of those values will be used in all safety analyses.

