7.5. Schedule of Assessments

Table 3, Table 4, Table 5, and Table 6 list the overall schedule of assessments for the study.

Table 3: Part 1: Schedule of Assessments for Patients in Cohorts 1 and 2

Assessment \ Study Week (Day)	Screen A ^a	Screen B ^a	Day 1 ^b	Week 1 (Phone) Day 3±1	Week 1 ^c Day 7±3	Week 2 (Phone) Day 10±1	Week 2 ^c Day 14±3	Week 3 (Phone) Day 21±3	Week 4 Day 28±3	Week 8 Day 56±3	Week 12 Day 84±3	Week 16 or End of Treatment Visit ^d Day 112±3	Follow-up ^d
Informed consent	X												
Inclusion/ exclusion	X		X ^e										
Demographics and baseline disease characteristics	X												
Concomitant medications	X		X	X	X	X	X	X	X	X	X	X	X
Medical history	X												
Height	X												
Weight in clinic	X		X		X		X		X	X	X	X	X
Weight at home			X ^f	X ^f	X ^f	X ^f	X ^f	X ^f	X ^f	X ^f	X ^f	X ^f	
Dispense weight diary			X		X		X		X	X	X	X	
Collect/review weight diary				X	X	X	X	X	X	X	X	X	
ECG	X											X	X
Vital sign measurements	X		X		X		X		X	X	X	X	X
Physical exam ^g /clinical worsening assessment ^h	X		X		X ⁱ		X ⁱ		X	X	X	X	X
Pregnancy test for WOCBP ^j	X		X									X	X
Study drug administration			X	-----X-----									
Dispense study drug			X						X	X	X		
Collect study drug									X	X	X	X	
Telephone contact				X		X		X					
Adverse event collection			X ^k	X	X	X	X	X	X	X	X	X	X
Clinical chemistry	X		X		X		X		X	X	X	X	X
BNP and NT-Pro BNP ^l	X		X		X		X		X	X	X	X	X
Hematology	X		X		X		X		X	X	X	X	X
Urinalysis and microscopy	X		X		X		X		X	X	X	X	X
Virus serology ^m	X												
6-min walk test	X ⁿ	X ⁿ							X ⁿ	X	X	X ⁿ	X
ECHO ^o	X ^p		X						X			X	
[REDACTED]			[REDACTED]						[REDACTED]			[REDACTED]	
[REDACTED]			[REDACTED]						[REDACTED]			[REDACTED]	
[REDACTED]			[REDACTED]						[REDACTED]			[REDACTED]	
[REDACTED]			[REDACTED]						[REDACTED]			[REDACTED]	

Assessment \ Study Week (Day)	Screen A ^a	Screen B ^a	Day 1 ^b	Week 1 (Phone) Day 3±1	Week 1 ^c Day 7±3	Week 2 (Phone) Day 10±1	Week 2 ^c Day 14±3	Week 3 (Phone) Day 21±3	Week 4 Day 28±3	Week 8 Day 56±3	Week 12 Day 84±3	Week 16 or End of Treatment Visit ^d Day 112±3	Follow-up ^d
24-hour ambulatory blood pressure monitoring (ABPM)		X ^s							X			X	
Pulmonary function testing/ Right Heart Catheterization	X ^t												
[REDACTED]	[REDACTED]	[REDACTED]							[REDACTED]	[REDACTED]	[REDACTED]	[REDACTED]	[REDACTED]
[REDACTED]			[REDACTED]									[REDACTED]	
Functional class assessment ^w	X		X									X	X
PK samples ^x									X				

^a Total screening period should not exceed 28 days.

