### 3.4.5.6 24 Hour Ambulatory Blood Pressure Monitoring

Systolic blood pressure, diastolic blood pressure, pulse pressure and heart rate are collected during the 24-hour ambulatory blood pressure monitoring (ABPM) [REDACTED]. Actual values and changes from baseline values for these four parameters will be summarized using descriptive statistics (including mean, standard deviation, quartiles, median, minima, maxima, and 95% confidence interval) by treatment group at all scheduled study visits. If the scheduled assessment is missing, the recheck measurement closest in time to scheduled visit will be used (if available).

The overall (24 hour) mean for each measure, the day time mean, and the night time mean will be summarized. Appendix A provides more detail of the planned analyses of the 24-hour ABPM data.

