### 3.4.5.7 ECG

Actual values for the 12-lead ECGs collected at each visit and changes from baseline in ECG measures (i.e., RR, PR, QRS, QT/QTc interval) at post-baseline visits will be summarized. Additionally, frequency counts for ECG results (normal, abnormal not clinically significant, abnormal clinically significant, or unable to evaluate) will be summarized at each visit. If the scheduled assessment is missing, use the recheck measurement closest in time to scheduled visit (if available).

## 3.5 Analysis of Part 2

All patients in Part 2 will receive an active dose of bardoxolone methyl. Patients must be compliant with dosing and complete Part 1 according to the protocol to be eligible for continuation into the extension period (Part 2). Therefore, separate populations for safety and efficacy will not be defined for Part 2 analyses.

The Part 2 safety and efficacy analyses will be summarized by randomized treatment, pooling all placebo patients and all active patients into various subgroups:

- All PAH patients (Cohorts 1, 2, 3a, and 3b patients)
- All CTD-PAH patients (CTD-PAH patients in Cohorts 1, 2, and 3a)
- All Non-CTD PAH patients (Non-CTD PAH patients in Cohorts 1, 2, and 3b)
- All PH patients (Cohorts 4a, 4b, 4c, 4d)

Due to the ongoing nature of this study, summary of Part 2 data will be strictly by patients initially randomized to active versus placebo patients that transition to active therapy. The groups will be labeled as BARD or PBO-BARD. All patients randomized to an active dose of bardoxolone methyl in Part 1 will be summarized with the BARD group in Part 2 analyses. All patients randomized to placebo in Part 1 will be summarized with the PBO-BARD group in Part 2 analyses.

Additional by-dose level results may be presented to explore long term trends by dose level, but will be included in an ad hoc manner.

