### 3.7.4 Analysis Windows for Unscheduled and End of Treatment Visits (Part 1)

Additionally, unscheduled assessments and end of treatment assessments will be used in efficacy and safety analyses if the unscheduled assessment was collected within the scheduled window below. Study day will be calculated for each unscheduled assessment and compared to the protocol defined study day for each visit. In general, analysis windows for unscheduled and end of treatment visits in Part 1 will be defined as follows:

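### The Week 16 ECG and ABPM summaries leave out early stoppers whose end-of-treatment visit falls before Day 99, and no combined end-of-treatment row is planned

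*SAP*

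**What the plan says.** SAP 3.4.5 summarises all safety results except adverse events at nominal Weeks 1, 2, 4, 8, 12 and 16. It states: "Missing data will not be imputed for safety analyses". For a patient who stops before Week 16 and has an EOT assessment, the rule is: "that EOT will be used in analysis for the nominal protocol visit most closely matching" that patient's schedule. SAP 3.7.4 confirms the scope: "unscheduled assessments and end of treatment assessments will be used in efficacy and safety analyses", provided they fall within the Table 2 windows.

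The measure-specific sections add no separate EOT summary. SAP 3.4.5.7 covers "Actual values for the 12-lead ECGs collected at each visit and changes from baseline in ECG measures", with counts of the ECG result category at each visit. SAP 3.4.5.6 summarises ABPM "by treatment group at all scheduled study visits". Both allow a recheck measurement where the scheduled one is missing.

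In the Part 1 schedules (Protocol 7.5, Tables 3 and 4), ECG is marked at Screen A, in the single column headed "Week 16 or End of Treatment Visit", and at Follow-up. ABPM (Table 3 only) is marked at Screen B, Week 4 and that same column. The table footnotes require early stoppers to return for the EOT assessments, so the data will exist.

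**The concern.** Filing an EOT result under the closest visit works for laboratory tests, vital signs and weight, because everyone has those at each clinic visit. It does not work for a measure taken only once on treatment. The protocol treats Week 16 and EOT as one assessment, and the SAP splits them. A stopper's ECG then sits in a row where nobody has a scheduled ECG, and the Week 16 row loses that patient.

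Stopping is not random. Protocol 8.4 lists clinical worsening and adverse events among the reasons for discontinuation. Protocol 5.1.2 places the excess fluid-overload risk seen in an earlier trial in the first three to four weeks of treatment. A patient whose EOT visit is that early cannot reach the Week 16 row. ECG and ABPM are named safety endpoints (Protocol 6.2.2; SAP 1.6.5), so selection enters the main between-arm summary of each at the end of treatment.

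**Working it through.** **Inputs.** SAP Table 2 windows for EOT visits: Week 1 = Days 2–10, Week 2 = 11–20, Week 4 = 21–42, Week 8 = 43–70, Week 12 = 71–98, Week 16 = 99–119. ECG and ABPM schedules come from Protocol Tables 3 and 4. The Week 16 target is Day 112. The plan gives no figure of its own to reproduce.

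**Step 1: assign each possible EOT day from Day 2 to Day 111.**

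| Row | Days | Count | ECG scheduled? | ABPM scheduled? |
|---|---|---|---|---|
| Week 1 | 2–10 | 9 | no | no |
| Week 2 | 11–20 | 10 | no | no |
| Week 4 | 21–42 | 22 | no | yes |
| Week 8 | 43–70 | 28 | no | no |
| Week 12 | 71–98 | 28 | no | no |
| Week 16 | 99–111 | 13 | yes | yes |

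The total is 9 + 10 + 22 + 28 + 28 + 13 = 110. Outside Week 16: 110 − 13 = 97, and 97/110 = 88%. For ECG, all 97 days land where no ECG is scheduled. For ABPM, 97 − 22 = 75 do. If only days before the protocol's Week 16 visit window (before Day 109) count as early, 10 of 107 days (9%) remain in Week 16.

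**Step 2: cross-check.** Assigning each day to the nearest target day (7, 14, 28, 56, 84, 112) also starts Week 16 at Day 99. The wording in SAP 3.4.5 and the Table 2 windows therefore agree on the boundary that matters.

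**Step 3: does other text return these values to Week 16?** Imputation is ruled out. The recheck sentences concern retests, whereas EOT has its own explicit rule. The Follow-up ECG comes four weeks after the last dose, so it does not replace the on-treatment one. For ABPM, the restriction to scheduled visits leaves it unclear whether a value mapped to Weeks 1, 2, 8 or 12 appears in any table.

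**Step 4: illustrative size.** The documents give neither a stopping rate nor ECG abnormality rates, so all rates here are assumptions. Planned Part 1 enrolment is 38 + 16 + 6 × 24 = 198. If 10–20% stop early, that is 198 × 0.10 ≈ 20 to 198 × 0.20 ≈ 40 patients. For that range this is an upper bound, since stoppers with EOT from Day 99 stay in Week 16. Nor would 198 form one row: the SAP 1.8 pools are 38 + 16 + 2 × 24 = 102 (PAH) and 4 × 24 = 96 (PH).

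Suppose a new clinically significant abnormality occurs in 2% of completers and in 10–15% of stoppers. The all-patient rate is (1 − d) × 2% + d × r:
- d = 10%, r = 10%: 0.9 × 2 + 0.1 × 10 = 2.8%
- d = 20%, r = 15%: 0.8 × 2 + 0.2 × 15 = 4.6%

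A row without any stoppers would show 2.0%. These are pooled rates and show no distortion between arms. If both arms share the same rates, the between-arm difference hidden is (difference in stopping proportions) × (r − 2%). It is zero when the arms stop equally. With 20% against 10% stopping and r = 15%, it is 0.10 × 13 = 1.3 percentage points.

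ABPM covers 38 + 16 = 54 planned patients, about 54/4 = 13.5 on placebo at 3:1.

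**The case against.** The strongest reply is that clinically important ECG findings are not lost. Protocol 11.3 and 11.6 make clinically significant ECG changes, or the diagnosis behind them, adverse events. Adverse events are exempt from the visit mapping, and SAP 3.4.5.1 includes events up to 30 days after the last dose for patients who discontinue. SAP 2.3 lists all collected data by patient. This stands: what is missing is an arm-level end-of-treatment summary of the measurements, not the individual signal.

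Matching by study day also keeps exposure comparable within a row, whereas a combined row would place an EOT value from Day 15 beside values from Day 112. That is a reason to add a row rather than replace the existing ones. ABPM keeps a scheduled Week 4 comparison, so the point is sharper for ECG.

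The SAP calls the study exploratory (1.9) and bases dose selection on the totality of data (1.5.2). Protocol 5.1.6 reports no QT increase in a thorough QT study up to 80 mg. These limit the consequence but do not justify leaving collected endpoint data out of the natural comparison. SAP 3.5.5 defers further detail to mock tables that are not available here, and those could contain such a row; the visible text does not call for one.

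A reader might infer that every early stopper is removed and that Week 16 holds completers only. Table 2 does not support this, because EOT visits on Days 99 to 119 enter Week 16. The completer definition in SAP 3.4.2 (last dose within two weeks before the Week 16 visit) narrows that exception without removing it. With a 7-day gap from last dose to EOT visit, last doses on Days 92 to 97 still yield a Week 16 value although they are more than 14 days before Day 112. A reader might also infer that values always move to an earlier visit; the rule is the closest visit, and 54 of the 110 days map to a later target day. Nor are the Week 1 to 12 ECG rows without any comparator: placebo stoppers and unscheduled ECGs from continuing patients fall there too, though as selected patients.

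**Conclusion.** The point holds in a limited form. Stoppers with an EOT visit before Day 99 are left out of the Week 16 ECG and ABPM summaries, and nothing visible in the SAP restores them to an end-of-treatment comparison. The Week 16 ECG summary is close to completers only.

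This rests on the schedules and windows alone and needs no assumption about rates. The 88% describes possible EOT days; the documents give no distribution of stopping times, so it cannot be read as a share of patients. The 20 to 40 patients and the 2.8–4.6% against 2.0% are illustrations under assumed rates, not trial data. Any bias between arms depends on how stopping differs by arm, which is unknown. The change is worth making because the endpoints are named, the data are collected anyway and the cost is small. Safety reporting is not otherwise defective on this account.

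**What to change.** Add to SAP 3.4.5.6 and 3.4.5.7, in words such as: *In addition to the by-visit rows, ECG and ABPM will be summarised by arm in a row labelled Week 16/End of Treatment (last on-treatment assessment). For patients who stop before Week 16 this row uses the EOT value, provided it was taken within a stated number of days after the last dose.*

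- State that limit. SAP 3.4.5.3 already sets one for eGFR, excluding values 14 or more days after the last dose.
- Show exposure at the assessment by arm, because the row mixes exposure times.
- Keep the by-visit rows.
- Report the ECG category as a shift from baseline to the new row. SAP 3.4.5.2 already plans baseline-to-Week-16 shift tables for chemistry and hematology, while ECG categories are only counted per visit.
- Reconcile SAP Appendix A, which takes the last ABPM collection for a visit, with SAP 3.4.5 and 3.7.4, which take the one closest to the target day. The two differ when a scheduled Week 4 ABPM and an EOT ABPM fall in the same window.

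The cost is SAP wording and one table shell, with no new data.

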9.1.2. Management of Elevated Transaminase Levels (ALT and/or AST)

Nearly all instances of elevated transaminases are expected to be asymptomatic. Check transaminase levels (as well as total bilirubin (TBL), GGT, alkaline phosphatase (ALP), and International Normalized Ratio (INR) within 48-72 hours during an unscheduled visit if the following occurs:

- ALT or AST levels > 3X ULN

Repeat testing every 72 to 96 hours until transaminase levels are below three times the ULN for at least one week or the patient withdraws consent.

Discontinue study drug administration permanently if any of the following occurs:

- ALT or AST > 8X ULN
- ALT or AST > 5X ULN for more than 2 weeks
- ALT or AST > 3X ULN and [TBL > 2 x ULN **or** INR > 1.5]
- ALT or AST > 3X ULN with the appearance of fatigue, nausea, vomiting, right upper quadrant pain or tenderness, fever, rash, and/or eosinophilia (> 5%); The hepatobiliary tree must be visualized (e.g., ultrasound, MRI) and assessed if a patient discontinues taking study drug secondary to elevated transaminase levels. Additional tests/studies may be warranted depending on the clinical presentation.

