#### **3.4.5.2 Laboratory Data**

Laboratory test results include clinical chemistry, hematology, and urinalysis. Continuous lab data, including actual values and changes from baseline, will be summarized using descriptive statistics (including mean, standard deviation, quartiles, median, minima and maxima) for chemistry and hematology parameters. If the scheduled assessment is missing, use the recheck measurement closest in time to scheduled visit (if available).

If a Day 1 laboratory collection occurred after the first dose of study drug, that lab value should not be used as the baseline lab value. The baseline lab value is the last laboratory value collected before study drug administration.

Shift tables will be provided to assess changes from normal to abnormal shifts from baseline to Week 16 for chemistry and hematology parameters.

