## 3.7 Missing and Partial Data

For the analysis of safety variables, partial dates may be imputed; otherwise, missing data will be treated simply as missing. However, if an AE onset date is missing, it will be imputed (see Appendix C). The algorithms for imputation of partial dates depend upon the parameter (see Appendix C). The central laboratory uses assays that have lower limits of detection (LLD). Continuous laboratory data results which are less than the lower limit of detection or above the upper limit of quantification will be imputed to the value of the lower or upper limit plus or minus one significant digit, respectively (e.g., if the result of a continuous laboratory test is  $< 20$ , a value of 19 will be assigned).

Imputation for missing efficacy data (i.e., 6MWD) is described with the efficacy analysis Section 3.4.4.

### 3.7.2 Analysis Windows for Part 1

For all Part 1 analyses of 6MWD, scheduled visits will be used regardless of study day, as well as any unscheduled or end of treatment visits within the visit windows listed in Section 3.7.4. If an unscheduled or EOT visit falls within the same window as a nominal study visit, the average of the two will be used. For subjects that prematurely discontinue treatment before Week 16 with a 6MWT recorded at the End of Treatment (EOT) assessment, that EOT 6MWD will be used in analysis for the nominal protocol visit most closely matching the subject's visit schedule.

For all other Part 1 efficacy and safety analyses, if multiple assessments fall within the same analysis visit, the assessment closest to the target study day specified in the protocol will be used. If two assessments are equidistant from a post-baseline target visit day, the earlier assessment will be used. Visits that do not occur in all versions of the protocol (i.e., Week 6) should be treated as unscheduled assessments.

### 3.7.3 Analysis Windows for Part 2

Part 2 assessments will be used in efficacy and safety analyses if the assessment was collected within the scheduled window below. Study day will be calculated for each assessment and compared to the protocol defined study day for each visit. In general, analysis in Part 2 will be defined as follows:

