**Table 2. Visit Windows for Unscheduled and End of Treatment Visits in Part 1**

Analysis Visit	Study Day	Analysis Window
Day 1	1	$\text{Study Day} \leq 1$
Week 1	7	$2 \leq \text{Study Day} \leq 10$
Week 2	14	$11 \leq \text{Study Day} \leq 20$
Week 4	28	$21 \leq \text{Study Day} \leq 42$
Week 8	56	$43 \leq \text{Study Day} \leq 70$
Week 12	84	$71 \leq \text{Study Day} \leq 98$
Week 16	112	$99 \leq \text{Study Day} \leq 119$

Records from unscheduled or end of treatment visits that do not fall within an analysis window will be listed, but will not be analyzed. Per Section 3.4.4, for the 6MWT analysis, if use of the visit windows yields more than one value for a particular visit, the average of the two or more values will be used for analysis. For all other analyses, including the eGFR and safety analyses, the value closest to the target study day should be used (Table 2).

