## 5. APPENDICES

### 5.1 Appendix A: Ambulatory Blood Pressure Monitoring (ABPM)

Throughout this section, “ambulatory blood pressure” refers to the systolic and diastolic pressures, pulse pressure, and heart rate as collected via 24-hour ABPM. If multiple 24-hour APBM collections occur for a nominal study visit, the last 24-hour APBM collection will be used in the analysis.

Three ambulatory blood pressure parameters will be calculated for each patient using the 24-hour ABPM data.

1. A patient’s mean 24-hour ambulatory blood pressure is calculated as the average of all valid measurements taken from the patient’s ambulatory blood pressure monitoring device.
2. A patient’s mean daytime ambulatory blood pressure is calculated as the average of all valid measurements taken from 6 am to 10 pm.
3. A patient’s mean nighttime ambulatory blood pressure is calculated as the average of all valid measurements taken from 10 pm to 6 am next day.

For a given 24-hour period average, the numerator is the sum of all valid ambulatory blood pressure measurements, while the denominator is the number of all valid blood pressure measurements.

Using each of the three ambulatory blood pressure parameters (24-hour, daytime, nighttime) calculated for each patient, actual values and change from baseline values will be summarized descriptively by received study drug at all scheduled study visits for all four ambulatory blood pressure assessments (systolic blood pressure, diastolic blood pressure, pulse pressure, heart rate). Descriptive summaries will include confidence intervals for each treatment group as well as the difference between the treatment group’s means. Additionally, blood pressure analyses described in Section 5.1 will be performed using the ABPM measurements.

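### The SAP gives conflicting rules for choosing among several safety values at one visit, and one of them can let a triggered retest displace the abnormal value that prompted it

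*SAP*

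**What the plan says.** Three rules appear in the SAP.

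- **Closest to target.** Section 3.4.5, which covers all safety data, states that "if retest values are available, all safety analyses should use the results closest to the target study day". Its tie-break is "If two values are equidistant from the target study day, the earliest of those values will be used in all safety analyses". Section 3.7.2 has the same rule for Part 1 ("if multiple assessments fall within the same analysis visit, the assessment closest to the target study day specified in the protocol will be used"), as does the note under Table 2 in 3.7.4 ("For all other analyses, including the eGFR and safety analyses, the value closest to the target study day should be used (Table 2"). Section 3.4.5.3 applies it to eGFR. None of these makes an exception when a valid scheduled value exists.
- **Recheck only if the scheduled value is missing.** Section 3.4.5.2 (laboratory) says "If the scheduled assessment is missing, use the recheck measurement closest in time to scheduled visit (if available". Sections 3.4.5.5 (vital signs) and 3.4.5.7 (ECG) use the same sentence. Section 3.4.5.6 (ABPM) says "If the scheduled assessment is missing, the recheck measurement closest in time to scheduled visit will be used (if available".
- **Last recording.** Appendix A, for ABPM, says "If multiple 24-hour APBM collections occur for a nominal study visit, the last 24-hour APBM collection will be used in the analysis".

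Section 3.4.5 also assigns results from unscheduled visits to the nearest nominal visit, so retests do enter the by-visit tables. Protocol 9.7 allows unscheduled visits to repeat abnormal laboratory tests. Protocol 9.1.2 requires transaminases to be checked "within 48-72 hours during an unscheduled visit if the following occurs", the trigger being ALT or AST above three times the upper limit of normal.

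**The concern.** When a visit has both a scheduled value and a repeat, the SAP does not settle which one is tabulated. Two programmers could each follow it and produce different laboratory, vital sign, ECG and ABPM tables.

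For transaminases the choice is not neutral, because the repeat exists only because the scheduled value was high. Closest-to-target can then drop the triggering value from that visit's mean and maximum and tabulate its follow-up instead. The visible laboratory plan in 3.4.5.2 has by-visit descriptive statistics and a baseline-to-Week 16 shift table, with no worst-post-baseline summary that would recover the displaced value.

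Safety and tolerability is a secondary objective. SAP 1.5.2 rests the dose-range recommendation on clinical judgement of all the data, including whether safety is acceptable, so these tables feed the main decision.

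**Working it through.** The plan states no figure on this point. The check compares what each rule selects and counts how often the selections differ.

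**Inputs**
- Visit window: target day ±3 (Protocol Tables 3 and 4), so 7 possible draw days.
- Retest: 48–72 hours, taken first as 2 or 3 days after the draw (Protocol 9.1.2).
- Frequency of ALT or AST above three times the upper limit: about 4–11% in earlier bardoxolone studies (Protocol 5.1.3).
- Tie-break: the earlier value (SAP 3.4.5).

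**Step 1. All three rules on one ABPM example.** Week 4, target Day 28, scheduled recording on Day 25, repeats on Days 28 and 30:

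| Rule | Recording selected |
|---|---|
| Closest to target | Day 28 |
| Recheck only if scheduled is missing | Day 25 |
| Last recording | Day 30 |

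**Step 2. When closest-to-target displaces a laboratory value.** Let the draw be k days early and the retest r days after the draw. The draw is k days from target and the retest |r − k| days. The retest is chosen when |r − k| < k, which is the same as 0 < r < 2k. A draw on or after the target day is never displaced, because the retest is then further away.

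| Draw | Condition | r = 2 or 3 | r = 4 or 5 | r ≥ 6 |
|---|---|---|---|---|
| 3 days early | r < 6 | displaced | displaced | kept (tie at 6) |
| 2 days early | r < 4 | displaced | kept (tie at 4) | kept |
| 1 day early | r < 2 | kept (tie at 2) | kept | kept |
| On target or late | never | kept | kept | kept |

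As a share of the 7 draw days:
- r = 2 or 3: 2/7 = 29% (4 of the 14 day-and-lag combinations).
- r = 4 or 5: 1/7 = 14%.
- r ≥ 6: 0.

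Week 4 (Day 28) and Week 16 (Day 112) give the same counts. Under the missing-only rule the count is 0 of 14. Example: a high ALT on Day 25 and a retest on Day 27 puts Day 27 in the Week 4 row under 3.4.5, and Day 25 under the ordinary reading of 3.4.5.2.

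**Step 3. Share of patients**, assuming one triggering scheduled value per affected patient:
- Lag 2–3 days: 4% × 2/7 = 1.1%; 11% × 2/7 = 3.1%.
- Lag 4–5 days: 4% × 1/7 = 0.6%; 11% × 1/7 = 1.6%.

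A 24-patient subcohort randomized 2:1 has 16 bardoxolone patients. At the shortest lag, 16 × 1.1% ≈ 0.2 to 16 × 3.1% ≈ 0.5 patients are expected to be affected.

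**Step 4. The Week 16 shift table.** SAP 3.4 ends Part 1 data at the Week 16 visit for patients who enter Part 2. Read literally, a retest after that visit can displace the Week 16 value only in patients who do not continue.

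**The case against.** **The rules can be read together.** The missing-value sentences do not say what happens when both values exist, so closest-to-target could fill that gap. This reading is possible for laboratory tests, vital signs and ECG. However, if closest-to-target already governed every case, four subsection sentences conditioned on missingness would add almost nothing. They also use a different anchor, the scheduled visit rather than the target day. The ordinary reading is that they limit when a recheck counts. A reader might infer that three rules collide for all safety data; the documents show that only for ABPM.

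**For ABPM, Appendix A may simply govern.** Section 3.4.5.6 points to it for detail, and the only ABPM repeat the protocol describes is one pre-randomization re-test after an unqualified recording (Table 3, footnote s). There the last recording agrees with the baseline definition in SAP 3.3. That limits the practical effect, but Appendix A is not confined to baseline and still contradicts 3.4.5, 3.7.2 and 3.7.4. The documents do not show ABPM being repeated because blood pressure was abnormal.

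**The 29% depends on when the clock starts.** Protocol 9.1.2 does not say whether the 48–72 hours run from the draw or from the result, and safety laboratory tests are analysed centrally (Protocol 6.2.2). This stands, and is why the longer lags are shown.

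**No bias has been shown.** This largely stands. Closest-to-target is prespecified and uses neither treatment nor value. Protocol 5.1.3 has elevations peaking two to four weeks after starting or increasing the dose, so a retest a few days later may be as high or higher. A reader might infer that the rule systematically hides liver signals or flatters blood pressure and ECG results; the documents support neither inference.

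**The signal is not lost.** This stands. All data go into by-patient listings (SAP 2.3), clinically significant changes are reported as adverse events (Protocol 11.6), and the safety committee reviews the collected safety laboratory data (Protocol 9.6.3).

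**Conclusion.** The concern holds as an unresolved conflict over which value is analysed. It is a direct contradiction for ABPM, which applies only to Cohorts 1 and 2 (38 + 16 = 54 planned patients), and a conflict on the ordinary reading for laboratory tests, vital signs and ECG.

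Its demonstrable effect on results is small. A triggering transaminase value can be displaced only after an early draw, for about 1–3% of bardoxolone patients at a 2–3 day lag, about half that at 4–5 days, and none at 6 days or more. This assumes even visit spread, one triggering scheduled value per affected patient, and the 4–11% from earlier studies carrying over. The actual share cannot be known from the documents. The direction of any shift in the tables is not established, and no efficacy result changes. The point is minor but worth settling before tables are programmed.

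**What to change.** State one hierarchy for all Part 1 by-visit safety tables: analyse the valid scheduled value, and use a repeat only if the scheduled value is missing or technically invalid, which includes an unqualified ABPM recording. Where several repeats qualify, name the anchor and tie-break once.

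Then align every place that now says otherwise: 3.4.5, 3.4.5.3 (eGFR), 3.7.2, the note under Table 2 in 3.7.4, and Appendix A. Changing 3.4.5 alone would leave closest-to-target standing in 3.7 and turn an ambiguity into a plain contradiction. Leaving 3.4.5.3 unchanged could let creatinine and the eGFR derived from it come from different samples at the same visit.

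A worst-post-baseline summary for laboratory values would be a useful addition, since it captures extremes whichever value is tabulated by visit. The hierarchy itself costs SAP wording and programming alignment only, with no change to data collection or patient management.
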